18.2.2 Collecting and Recording Adverse Events and Pregnancy

Adverse events may be identified during this study through any of these methods:

- Examination of the participant during study visits.
- Questioning the participant during study visits.
- Receiving a safety contact from the participant at any time during the study

Note: participants will be asked to call the site if they develop any of the following:

- Illness or treatment from a physician or emergency department the entire duration of the study;
- Any adverse event that limits self-care activities of daily living (e.g. bathing, dressing and undressing, feeding self, using the toilet, taking medications, and not bed ridden) even if he/she decides not to seek medical care
- Local AEs and/or systemic AEs of grade 3 or higher related to phlebotomy, lymph node FNA, or bone marrow aspiration up to 7 days after the procedure will be recorded and reported within 7 days to ISM.
- Any SAEs for duration of study
- Any SARs of Code 3 or higher related to phlebotomy, lymph node FNA, or bone marrow aspiration up to 7 days after the procedure will be recorded and reported within 7 days to ISM.
- Any unexpected adverse events grade 3 or higher related to phlebotomy, lymph node FNA, or bone marrow aspiration up to 7 days after the procedure will be recorded and reported within 7 days to ISM.
- Anaphylaxis or anaphylactic shock up to 7 days after receiving vaccine dose and any acute complication or sequelae (including death) of anaphylaxis (interval - not applicable)
- Shoulder Injury Related to Vaccine Administration up to 7 days after receiving vaccine dose and any acute complication or sequelae (including death) of shoulder injury (interval - not applicable)
- Vasovagal syncope up to 7 days after receiving vaccine dose and any acute complication or sequelae (including death) of vasovagal syncope (interval - not applicable)
- Events described in manufacturer's package insert (Appendix C) as contraindications to additional doses of vaccine: hypersensitivity, including severe allergic reactions to yeast (a vaccine component), or after previous dose of Gardasil 9 or Gardasil

A complete recording of safety events in the CRF will include event term; date(s) of onset and resolution/stabilization; assessment of severity; relationship to procedures/intervention(s) such as phlebotomy, FNA, or bone marrow aspiration;

Protocol Title: Assessing immunological basis of durable antibody responses to 9-valent HPV vaccination

expectedness; determination of whether the AE qualifies as serious or non-serious; treatment required; action taken with study participation; and outcome. AEs qualifying as serious also require a narrative of the event. Updates in safety events will be recorded as additional information becomes available.

Information on pregnancies will be collected from the time a participant signs the consent until the participant completes study participation.

If a participant becomes pregnant after study entry, the investigator will discuss with the participant and/or the treating physician the known possible risks to the fetus.

Participants becoming pregnant after study entry will be withdrawn from the study and followed until the end of the pregnancy. A pregnancy resulting in congenital anomaly/birth defect will be considered a SAE. Any premature termination of the pregnancy will also be reported and assessed as an SAE as needed.

18.3 Grading and Attribution of Adverse Events

18.3.1 Grading Criteria

Adverse events will be graded according to the criteria set forth in the National Cancer Institute's Common Terminology Criteria for Adverse Events Version 5.0 [November 27, 2017; <http://evs.nci.nih.gov/ftp1/CTCAE/About.html>]

This document (referred to herein as the NCI-CTCAE manual) provides a common language to describe levels of severity, to analyze and interpret data, and to articulate the clinical significance of all adverse events.

All adverse events whether or not listed in the NCI-CTCAE will be graded on a scale from 1 to 5 according to the following standards in the NCI-CTCAE manual (A semi-colon indicates 'or' within the description of the grade):

- Grade 1 Mild; asymptomatic or mild symptoms; clinical or diagnostic observations only; intervention not indicated.
- Grade 2 Moderate; minimal, local or noninvasive intervention indicated; limiting age-appropriate instrumental ADL*.
- Grade 3 Severe or medically significant but not immediately life-threatening; hospitalization or prolongation of hospitalization indicated; disabling; limiting self-care ADL**.
- Grade 4 Life-threatening consequences; urgent intervention indicated.
- Grade 5 Death related to AE.

*Instrumental Activities of Daily Living (ADL) refer to preparing meals, shopping for groceries or clothes, using the telephone, managing money, etc.

Protocol Title: Assessing immunological basis of durable antibody responses to 9-valent HPV vaccination

**Self-care Activities of Daily Living (ADL) refer to bathing, dressing and undressing, feeding self, using the toilet, taking medications, and not bedridden.

Not all Grades are appropriate for all AEs; therefore, some AEs are listed with fewer than five options for Grade selection.

Anaphylaxis is a disorder characterized by an acute inflammatory reaction resulting from the release of histamine and histamine-like substances from mast cells, causing a hypersensitivity immune response. Clinically, it presents with breathing difficulty, dizziness, hypotension, cyanosis and loss of consciousness and may lead to death.

Severity grading of anaphylaxis as per the NCI-CTCAE manual is as follows:

- Grade 1= not applicable
- Grade 2= not applicable
- Grade 3= Symptomatic bronchospasm, with or without urticaria; parenteral intervention indicated; allergy-related edema/angioedema; hypotension
- Grade 4= Life-threatening consequences; urgent intervention indicated
- Grade 5= Death

Severity grading of AEs of laboratory abnormalities will be assessed as per the NCI-CTCAE manual.

18.3.2 Definition of Attribution

The site investigator will initially determine the relationship of an adverse event grade 3 and above to study procedures.

The relationship of an AE to study participation will be determined using definitions in the table below:

Code	Descriptor	Definition (guidelines)
UNRELATED CATEGORY		
1	Unrelated	The adverse event is clearly not related to study. The event is completely related to an etiology other than the study product or study intervention (the alternative etiology must be documented in the study participant's medical record)
2	Unlikely	The adverse event is doubtfully related to study and likely to be related to factors other than study product or study intervention.
RELATED CATEGORIES		

3	Possible	The adverse event may be related to study. There is an association between the event and the administration of study product or between the event and a study procedure and there is a plausible mechanism for the event to be related to the study product or procedure. There may be also an alternative etiology, such as characteristics of the participant's clinical status and/or underlying disease
4	Probable	The adverse event is likely related to study. There is (1) an association between the event and the administration of study product or study intervention, (2) a plausible mechanism for the event to be related to the study product or study procedure, and (3) the event could not be reasonably explained by known characteristics of the participant's clinical status and or an alternative etiology is not apparent
5	Definite	The adverse event is clearly related to study. There is (1) an association between the event and the administration of the study product or study intervention, (2) a plausible mechanism for the event to be related to the related to the study product or study procedure, and (3) causes other than the study product have been ruled out and/or the event re-appeared on re-exposure to the study product

18.3.3 Reporting Timelines

- Reporting Serious Adverse Events to the Independent Safety Monitor**

The Principal Investigator will notify the ISM by email of any SAE within 24 hours of becoming aware of the event. The ISM may request further information if necessary and possibly request changes to the protocol or consent form as a consequence of the adverse event.

- Notifying Institutional Review Board**

The Principal Investigator will ensure the timely dissemination of SAE information, including SAEs requiring expedited review by the ISM and to the IRB in accordance with IRB regulations and guidelines. Serious adverse events that are unanticipated, related to study participation, and involving risk to participant or others will be reported to the IRB promptly per IRB guidelines.

18.4 Stopping Rules

18.4.1 Study Stopping Rules:

Study procedures will be suspended pending expedited review of all pertinent data by the institutional review board and the ISM if Gardasil 9, lidocaine, or lorazepam were recalled by the manufacturer.

Also, procedures will be suspended pending review of all pertinent data by the PI and the ISM after the occurrence of any of the following:

- 1 case of infection at the site of lymph node sampling.
- 2 cases of hematomas at the site of lymph node sampling.
- 1 case of pneumothorax from lymph node sampling.
- 1 case of persistent (>4 weeks) paresthesia or numbness in upper extremity due to lymph node sampling.
- 1 case of persistent (>4 weeks) decreased range of motion due to lymph node sampling.
- Bone marrow aspiration-related grade 3 AE or SAE

18.4.2 Individual Participant Stopping Rules:

Early study termination will occur in participants due to any of the following circumstances detailed in **Section 14**.

18.4.3 Early Termination From Study Procedures with Continued Study Participation/Follow-up:

Please refer to **Section 14**.

18.4.4 Follow-up After Early Study Termination:

Participants who are prematurely terminated from the study due to an AE will be followed until resolution of the AE or until 28 days after a participant terminates from the study, or 7 days after a participant undergoes lymph node or bone marrow sampling, whichever comes later. Resolution of an AE is defined as the return to baseline status or as stabilization of the condition with the expectation that it will remain chronic.

After assessing terminated participants for safety under the provisions stated above, the participant will be seen in clinic, if necessary.

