18.2.1 Safety Reporting

- **Adverse Events (AE)**

Adverse event means any untoward medical occurrence associated with the use of a drug in humans, whether or not considered drug related.

An adverse event (also referred to as an adverse experience) can be any unfavorable and unintended sign, symptom, or disease temporally associated with the use of the procedure, without any judgment about causality.

After 9-valent vaccination, the following adverse events in the indicated intervals must be reported to Vaccine Adverse Event Reporting System (VAERS).

- Anaphylaxis or anaphylactic shock (7 days)
- Shoulder Injury Related to Vaccine Administration (7 days)
- Vasovagal syncope (7 days)
- Any acute complication or sequelae (including death) of above events (interval - not applicable)
- Events described in manufacturer's package insert (Appendix C) as contraindications to additional doses of vaccine: hypersensitivity, including severe allergic reactions to yeast (a vaccine component), or after previous dose of Gardasil 9 or Gardasil

Any grade 3 or higher adverse event (up to 7 days after phlebotomy, lymph node FNA, or bone marrow aspiration) will be recorded and reported within a week to Independent Safety Monitor (ISM).

- **Suspected Adverse Reaction (SAR)**

Suspected adverse reaction means any adverse event for which there is a reasonable possibility that the drug or procedure caused the adverse event.

Suspected adverse reaction implies a lesser degree of certainty about causality than adverse reaction, which means any adverse event caused by a drug.

SARs after vaccine administration may include:

- Local reactions: injection site redness, injection site swelling, pain at the site of injection, itching of the skin at the injection site.
- Systemic reactions: headache, fever, nausea, dizziness.

SARs after phlebotomy may include:

Protocol Title: Assessing immunological basis of durable antibody responses to 9-valent HPV vaccination

- Local reactions: pain at the site of venipuncture, bruising at the site of venipuncture, infection at the site of venipuncture
- Systemic reactions: lightheadedness or fainting

SARS after lymph node FNA procedure may include:

- Local reactions: pain at the site of aspiration, bruising of the skin at the site of aspiration, bleeding and hematoma formation at the site of aspiration, infection at site of aspiration, numbness caused by accidental nerve damage, pneumothorax (collapsed lung)

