- Systemic reactions: Vaso-vagal response (lightheadedness or fainting) or allergic reaction to anesthetic

SARSS after bone marrow aspiration may include:

- Local reactions: pain at the site of aspiration, bruising at the site of aspiration, infection at the site of aspiration
- Systemic reactions: mild transient anemia, lightheadedness, nausea, transient low blood pressure, or allergic reaction to anesthetic

Any SAR of Code 3 or higher related to phlebotomy, lymph node FNA, or bone marrow aspiration up to 7 days after the procedure will be recorded and reported within 7 days to ISM.

• **Serious Adverse Event (SAE) or Serious Suspected Adverse Reaction**

An adverse event or suspected adverse reaction is considered “serious” if, in the view of the investigator, it results in any of the following outcomes:

- **Death.**
- **A life-threatening adverse event.**
- **Inpatient hospitalization or prolongation of existing hospitalization.**
- **A persistent or significant incapacity or substantial disruption of the ability to conduct normal life functions.**
- **A congenital anomaly/birth defect.**

Important medical events that may not result in death, be life-threatening, or require hospitalization may be considered serious when, based upon appropriate medical judgment, they may jeopardize the participant and may require medical or surgical intervention to prevent one of the outcomes listed in this definition. Serious adverse events will be recorded for the entire duration of the study and reported within 24 hours to ISM, and also to IRB if study related.

An adverse event or suspected adverse reaction is considered “life-threatening” if, in the view of the investigator, its occurrence places the patient or participant

Protocol Title: Assessing immunological basis of durable antibody responses to 9-valent HPV vaccination

at immediate risk of death. It does not include an adverse event or suspected adverse reaction that, had it occurred in a more severe form, might have caused death.

- **Unexpected Adverse Event or Unexpected Suspected Adverse Reaction**

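### The adverse event recording rules do not guarantee that every lymph node sampling event that triggers suspension under section 18.4.1 is recorded

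*Protocol*

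**What the plan says.** **Stopping rules (Protocol 18.4.1).** Procedures are suspended pending review by the principal investigator and the independent safety monitor (ISM) after any of several FNA events. One site infection is enough. So are "2 cases of hematomas at the site of lymph node sampling", "1 case of persistent (>4 weeks) paresthesia or numbness in upper extremity due to lymph node sampling", or one case of reduced range of motion lasting more than 4 weeks. None of these carries a severity grade or a limit on onset.

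**Recording rules (Protocol 18.2.1 and 18.2.2).**
- Adverse events: "Any grade 3 or higher adverse event (up to 7 days after phlebotomy, lymph node FNA, or bone marrow aspiration) will be recorded" and reported to the ISM within a week.
- Suspected adverse reactions (SARs): "Any SAR of Code 3 or higher related to phlebotomy, lymph node FNA, or bone marrow aspiration up to 7 days after the procedure" are recorded and reported.
- Unexpected events: the same 7-day window, with a threshold of grade 3.
- Serious adverse events: recorded for the whole study.
- Section 18.2.2 lists what participants are asked to phone in. It repeats these rules, including "Local AEs and/or systemic AEs of grade 3 or higher related to phlebotomy, lymph node FNA, or bone marrow aspiration", and adds serious events, named vaccine events and anything that limits self-care.

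**Attribution (Protocol 18.3.2).** Code 3 in the table is a relationship category, Possible; it is not a severity grade. The section opens: "The site investigator will initially determine the relationship of an adverse event grade 3 and above to study procedures". Its next sentence refers to the relationship of an adverse event with no grade limit.

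**The concern.** A stopping rule works only if the events it counts reach the people who apply it. Here the trigger list and the recording rules use different criteria. The triggers are any-grade events and long-lasting symptoms; the recording rules filter on grade or code and close after 7 days. Staff who follow section 18.2 exactly could leave a qualifying FNA event off the case report form and out of the reports to the ISM.

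At stake is the suspension boundary for invasive sampling of healthy volunteers, and the completeness of the cumulative safety data that section 22.1 says the ISM reviews monthly. The bone marrow trigger is much less affected. It is itself set at grade 3 or serious, which matches the recording threshold, and section 6.6.4 schedules a call 7 days after the aspirate.

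**Working it through.** The protocol states no figure to reproduce. The check sets each FNA trigger against each recording route, for events that are **not serious**.

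| Event that can meet 18.4.1 | Grade 3+ rule, 7 days | SAR Code 3+ rule, 7 days | Result |
|---|---|---|---|
| Infection or haematoma, grade 1–2, onset by day 7 | No | Yes, if a code is assigned | Depends on Code 3 |
| Numbness or paresthesia, grade 1–2, onset by day 7 | No | Yes, if a code is assigned | Depends on Code 3; the resolution date can then show more than 4 weeks |
| Reduced range of motion, grade 1–2, onset by day 7 | No | Not named in the FNA reaction list, though that list is open-ended | Depends on Code 3 and on being treated as a SAR |
| Any of these, any grade, onset after day 7 | No | No | No recording rule applies |

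**Why the Code 3 route is uncertain.**
1. Under 18.2.1 a SAR already requires a reasonable possibility of causation, so a threshold at Possible excludes almost nothing. Read literally, the rule takes in low-grade haematoma, infection and numbness within 7 days.
2. The parallel sentences for adverse events and for unexpected events say grade 3. If Code 3 is a slip for grade 3, the low-grade route disappears.
3. The first sentence of 18.3.2 has relationship determined for grade 3 and above. On that reading a grade 1–2 event never receives a code. The second sentence has no such limit, so the section is ambiguous.

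**Timing.** The recording window ends at day 7. A duration of more than 4 weeks cannot be met until after day 28, which is 28 − 7 = 21 days later at the earliest. This does not matter for an event already on the form, but nothing obliges staff to open an entry for a later onset.

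Gap from the last FNA to the next scheduled visit, from section 6.3 and Appendix A:
- Group 1: D30 to D60 = 30 days. With ±5 on each visit, 55 − 35 = 20 to 65 − 25 = 40.
- Group 2: Visit 8 + 30 (nominally D90) to D180 = 90 days. The FNA can fall on D80 to D100 and the visit on D175 to D185, giving 75 to 105.
- Group 3: Visit 13 + 30 (nominally D210) to D365 = 155 days. The FNA can fall on D200 to D220 and the visit on D351 to D379, giving 131 to 179.

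**Illustration of the grade 3+ route alone.** The rates below are assumptions; the documents give none. There are 16 × 3 = 48 FNAs. With probability p per FNA, P(2 or more) = 1 − (1 − p)^48 − 48p(1 − p)^47.

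| Assumed haematoma rate | Any grade | If 50% reach grade 3 | If 10% reach grade 3 |
|---|---|---|---|
| 5% | 1 − 0.0853 − 0.2154 = 0.699 | p = 0.025: 0.338 | p = 0.005: 0.024 |
| 2% | 1 − 0.3792 − 0.3714 = 0.249 | p = 0.01: 0.083 | p = 0.002: 0.004 |

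The contrast is driven by the assumed grade 3 share and supposes that the Code 3 route records nothing. If that route works as literally written, the gap for haematomas with onset by day 7 closes.

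**The case against.** The case on the other side is substantial.

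- **Stopping turns on occurrence.** Section 18.4.1 does not require a form entry, and detection is broad. Participants are told to call about any FNA complication (6.3), are examined and questioned at visits (18.2.2), and all adverse events are to be graded (18.3.1). An investigator who knows of a grade 1 haematoma may count it. That stands, so failure to stop is not inevitable. But none of these provisions requires the event to be recorded or sent to the ISM.
- **More is recorded than grade 3+ events.** A reader might infer that nothing below grade 3 is ever recorded. The documents do not support that: serious events are recorded throughout, and the Code 3 rule, taken literally, covers low-grade FNA reactions within 7 days.
- **Duration is not lost for recorded events.** A reader might infer that symptoms lasting over 4 weeks lie wholly outside the 7-day window. They do not if onset is by day 7 and an entry is opened, because 18.2.2 requires onset and resolution dates and later updates.
- **The 18.2.2 list is not an exclusive rule.** A reader might infer that it keeps only procedure-related events, so that a grade 3 vaccine reaction is in under 18.2.1 and out under 18.2.2. It is a call-in list and includes events that limit self-care, a feature of grade 3 under 18.3.1. What remains is a lack of clarity. Under 18.2.1 such a reaction is recorded because blood is also drawn at vaccination visits, and 18.2.2 does not say whether the self-care item leads to recording.
- **Other safeguards exist.** Section 13.6 allows withdrawal after a related grade 3 event, and the ISM has monthly reports. Both depend on what is recorded or graded 3, so they do not close the gap.

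**Conclusion.** The point holds as a conflict between stated rules. Following section 18.2 exactly does not guarantee that every FNA event named in 18.4.1 is recorded.

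One gap survives every reading: a non-serious FNA infection, haematoma, numbness or reduced motion first appearing after day 7 has no recording rule. A second gap, for grade 1–2 events within 7 days, exists only if Code 3 means grade 3 or if codes are given only to grade 3+ events; the text leaves both open. Late events rely on self-report, with 30, 90 or 155 nominal days to the next scheduled visit after the last FNA.

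How often this would hide a trigger cannot be derived from the documents, which call FNA risks rare and give no complication rates. The binomial figures illustrate one route under assumed rates and do not estimate the trial's risk. The point deserves correction, but it does not show that the stopping rules cannot work.

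**What to change.** Reconcile sections 18.2.1, 18.2.2, 18.3.2 and 18.4.1:
- Require every event named in 18.4.1 to be recorded, attributed and reported to the ISM, whatever its grade or onset day.
- Keep each such entry open until the event resolves or the duration stated in its stopping rule has been established. For Groups 2 and 3 the existing visit schedule alone will not do this after the last FNA, so the text should say how open events are followed between visits.
- State whether Code 3 means a severity grade or an attribution code, and make 18.3.2 say which events receive a code.
- State once whether grade 3 or higher events after vaccination are recorded.

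The stopping thresholds stay as they are. The cost is a wording amendment, slightly more case report form entry, and follow-up contact for the events that remain open.

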14.3 Risks of Study Procedures

The potential risks to participants are those associated with having blood drawn, the risks associated with lymph node fine needle aspiration, and the risks associated with bone marrow aspiration.

14.3.1 Blood draws:

Blood sample collection involves transient discomfort and may cause fainting, which is managed by having the participant lie down prior. The blood draw site may bruise, and this can be ameliorated by holding pressure to this site following the blood draw. The sites of blood draw are potential sites of infection, but this risk is made very unlikely by the use of sterile technique.

14.3.2 Finger prick:

Blood sample collection by finger prick and absorption with a microsampler device is an optional procedure that involves transient discomfort and may cause fainting, which is managed by having the participant sit or lie down prior. The blood draw site may bruise, and this can be ameliorated by holding pressure to this site following the

Protocol Title: Assessing immunological basis of durable antibody responses to 9-valent HPV vaccination

blood draw. The sites of blood draw are potential sites of infection, but this risk is made very unlikely by the use of sterile technique.

14.3.3 Saliva collection:

The procedure to obtain saliva is analogous to brushing one's teeth and there is essentially no risk involved.

14.3.4 Fine needle aspiration (FNA) of the lymph node:

Fine needle aspirates are generally tolerated very well, with most (n = 8/13) experiencing no discomfort to mild discomfort²⁸. The potential risks for fine needle aspiration are rare. They include, but are not limited to: tenderness around aspiration site, bruising, bleeding and hematoma formation, as well as much rarer complications: infection, vagal reaction, numbness caused by accidental nerve damage, and pneumothorax (for axillary lymphadenopathy sampling).²⁹⁻³¹

14.3.5 Bone marrow aspiration:

The physical risks of undergoing a bone marrow aspiration are pain and bruising that may last 1 to 3 days. Very rarely more serious side effects could occur including damage to normal blood vessels, veins or bone structures or rarely localized infection at the area where the marrow is removed. The removal of 40 ml or less of marrow produces a temporary and mild transient anemia³². A small number of participants experience vaso-vagal response including, lightheadedness, nausea, and transient hypotension.

14.4 Loss of Confidentiality:

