An adverse event or suspected adverse reaction is considered “unexpected” if it is not listed in the Summary of Product Characteristics or is not listed at the specificity or severity that has been observed; or, if the Summary of Product Characteristics is not required or available, is not consistent with the risk information described in the general investigational plan or elsewhere in the current application, as amended.

For example, under this definition, hepatic necrosis would be unexpected (by virtue of greater severity) if the investigator brochure referred only to elevated hepatic enzymes or hepatitis. Similarly, cerebral thromboembolism and cerebral vasculitis would be unexpected (by virtue of greater specificity) if the investigator brochure listed only cerebral vascular accidents.

“Unexpected,” as used in this definition, also refers to adverse events or suspected adverse reactions that are mentioned in the Summary of Product Characteristics as occurring with a class of drugs or as anticipated from the pharmacological properties of the drug, but are not specifically mentioned as occurring with the particular drug under investigation.

Any unexpected adverse event grade 3 or higher related to phlebotomy, lymph node FNA, or bone marrow aspiration up to 7 days after the procedure will be recorded and reported within 7 days to ISM.

- **Independent Safety Monitoring**

The ISM is a physician with relevant expertise in clinical studies whose primary responsibility will be to provide independent safety monitoring in a timely fashion and to provide recommendations regarding the safe continuation of this study.

The ISM will evaluate safety data generated from study participants against the known safety profile of the study product or study procedure to assess for possible changes to the overall risk of the study.

The ISM will communicate with the Principal Investigator as needed. The study has provisions for a back-up ISM to ensure that independent safety monitoring happens at all times during the study.

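### Section 18.4.1 suspends procedures after any marrow-related grade 3 AE or SAE but has no such trigger for lymph node FNA, so after one severe haematoma or an unlisted serious FNA event a pause is only discretionary.

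*Protocol*

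**What the plan says.** Section 18.4.1 lists the events after which procedures stop until the PI and the ISM have reviewed the data. For marrow the trigger is based on severity: "Bone marrow aspiration-related grade 3 AE or SAE". For FNA there are five named complications:

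- one infection at the sampling site;
- "2 cases of hematomas at the site of lymph node sampling";
- one pneumothorax;
- one case of numbness or paresthesia lasting more than 4 weeks;
- one case of reduced range of motion lasting more than 4 weeks.

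Section 18.2.1 lists the reactions expected after each procedure. After FNA these include "Systemic reactions: Vaso-vagal response (lightheadedness or fainting) or allergic reaction to anesthetic". After marrow aspiration the systemic list ends with "transient low blood pressure, or allergic reaction to anesthetic".

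Severe events also reach the ISM by report. Section 18.3.3 states: "The Principal Investigator will notify the ISM by email of any SAE within 24 hours of becoming aware of the event". Under section 18.2.1, a grade 3 or higher AE within 7 days of phlebotomy, FNA or marrow aspiration goes to the ISM within a week. The ISM's role is to "provide recommendations regarding the safe continuation of this study".

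**The concern.** The marrow rule catches any severe event, whatever its nature. The FNA rule catches only what its authors thought to list, with nothing behind the list for a severe event of another kind. Two cases fall through: one severe haematoma, which is on the list but below its count, and a serious reaction that is not on the list at all.

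What is at stake is whether a pause is automatic or left to judgement. After such an event nothing obliges further FNAs in healthy volunteers to wait for review. If the event is grade 3 but not serious, the ISM may not hear of it for up to a week, and procedures may continue in the meantime.

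**Working it through.** The protocol states no figure for the stopping rule, so there is nothing to reproduce. The check sets its sections side by side.

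**Step 1: match the reactions to the triggers.** Section 18.2.1 names six local FNA reactions and two systemic ones: 6 + 2 = 8. Against section 18.4.1:

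| FNA reaction (18.2.1) | Suspends procedures under 18.4.1? |
|---|---|
| Infection | Yes, one case |
| Pneumothorax | Yes, one case |
| Bleeding and haematoma | Only at the second haematoma |
| Numbness | Only if over 4 weeks |
| Pain | Never |
| Bruising | Never |
| Vaso-vagal response | Never |
| Allergic reaction to anaesthetic | Never |

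That gives 2 on a single case, 2 under a condition and 4 never: 2 + 2 + 4 = 8. The fifth FNA trigger, reduced range of motion, has no counterpart in the reaction list. None of the five FNA triggers refers to grade or seriousness; the single marrow trigger refers to both.

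**Step 2: run specific events through the rule.**

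- *One haematoma leading to hospital admission.* Section 18.2.1 makes this an SAE. The haematoma count is one, the threshold is two, and no other FNA trigger applies. No suspension is required.
- *Anaphylaxis to lidocaine.* Sections 5.1.2 and 5.2.2 provide for lidocaine in both procedures. Section 18.3.1 gives anaphylaxis no grade 1 or 2; it starts at grade 3. Attributed to marrow aspiration, it meets the marrow trigger. Attributed to FNA, it meets none.
- *Vaso-vagal collapse with serious injury after FNA.* No trigger.

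**Step 3: look for another section that requires a pause.**

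- 18.2.1 and 18.3.3 require reporting to the ISM, not suspension.
- 18.3.3 lets the ISM ask for information or for protocol changes; neither is a mandatory pause.
- 13.6 lets the PI withdraw the affected participant after a procedure-related grade 3 AE or SAE. It is discretionary and concerns one person.
- 18.4.2 and 18.4.3 concern individual participants and refer to section 14, which describes risks and contains no pause rule.
- The recall trigger in 18.4.1 needs action by a manufacturer.
- 22.1 gives the ISM monthly cumulative reports, again without a pause.

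None closes the gap.

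**Step 4: exposure.** Section 1 plans 16 participants, three FNAs each, and marrow sampling at D730 and D1825. FNAs: 16 × 3 = 48. Marrow aspirates, not counting re-attempts: 16 × 2 = 32. The procedure without the severity trigger is the more frequent one.

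**The case against.** The two rules differ by design, and nothing in the protocol says they must match. In several respects the FNA list is the stricter: one infection or one pneumothorax of any grade stops procedures, mild haematomas count towards the two, and persistent numbness or loss of motion counts at any grade. That is right, and it is a reason to keep the list.

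The anaesthetic example is partly covered for the individual. Lidocaine allergy is an exclusion (10.2.6), eligibility is checked again before each FNA (6.3), and a participant who no longer qualifies may be terminated (13.1). This protects the person who reacted. It does not require anyone to review the event before the next participant's FNA.

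The settings are also not identical. Marrow aspiration may use 1–2% lidocaine and lorazepam, whereas FNA uses 1% lidocaine. The protocol does not offer this as the reason for the different rule.

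The one-week delay does not apply to the hospitalised haematoma, which is an SAE and reaches the ISM within 24 hours. The week is the outer limit for non-serious grade 3 events, and it is the same for marrow.

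The count of four reactions that never trigger includes pain and bruising, where a severe case may be unlikely. The practical gap is one severe haematoma or an unlisted serious event.

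Finally, section 14.3.4 says "The potential risks for fine needle aspiration are rare", and the exclusions for bleeding risk (10.2.14) and lidocaine allergy lower them further. That limits how often the gap would matter. The reporting and discretionary routes cover marrow too, and an automatic trigger was still adopted there, so they do not explain its absence for FNA.

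**Conclusion.** The concern holds as a modest safety point. Section 18.4.1 has no grade or SAE backstop for FNA, and no other section makes a study pause mandatory after one severe haematoma or an unlisted serious FNA event. Such events would be seen by the ISM, and the PI or ISM could choose to pause, so the difference is automatic versus discretionary.

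The conclusion rests on the wording of the rule alone. It needs no assumed event rate, and none is given in the protocol, so the chance of meeting the gap over 48 FNAs is not estimated. The gap in the text is certain; its practical importance is limited.

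**What to change.** Add one bullet to section 18.4.1: *Lymph node FNA-related grade 3 or higher AE or SAE*, with the same review by the PI and ISM. Keep all five existing FNA triggers unchanged, including the two-haematoma rule, because they catch milder events that a severity trigger would miss.

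The cost is one line in a protocol amendment. Reviewers and safety reports are already in place, and the only operational burden is an occasional extra pause after a severe event. The protocol does not state enrolment status. If all FNAs are already done, the line matters only if enrolment expands (section 6, Study Design) or participants are replaced (section 18.4.5).
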